Subjects in the KCI arm of this clinical study will receive NPWT alone (standard of care) until wound closure with the following two KCI devices that are both FDA cleared as Class II devices under Product Code OMP for the same indication and intended for the control subject group in this clinical study. In the acute care setting, patients will be treated with the KCI VAC Ulta NPWT device. In the home environment, patients will be treated with the KCI VAC Via NPWT system, paid for by the study at no cost to the subjects.

KCI USA, Inc. V.A.C.Ulta™ Negative Pressure Wound Therapy System (K100657). It includes a NPWT powered suction pump and a sterile dressing system applied to the wound, which is connected via tubing to a therapy unit that generates negative pressure at the wound. A sterile, disposable canister collects wound exudates removed via the negative pressure. The dressing utilizes an open-cell polymer foam dressing that conforms to the wound bed. When sealed and placed under negative pressure, the system creates an environment that has been shown to promote the wound healing process, reduce edema, prepare the wound bed for closure, promote the formation of granulation tissue and remove infectious materials. The V.A.C. Ulta NPWT System is indicated for patients with chronic, acute, traumatic, sub-acute and dehisced wounds, partial-thickness burns, ulcers (such as diabetic, pressure and venous insufficiency), flaps and grafts.

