Osteomyelitis will be diagnosed when radiographic and clinical signs are consistent with bone infection. This diagnosis will be confirmed with imaging, bone biopsy, culture or histopathology as most applicable to the individual subject. The bacterial pathogens and sensitivities from bone and soft tissue cultures will be recorded and direct antibiotic therapy applied, if necessary [79].

Study Procedures

Procedures and Evaluations During the Research

The time period from Day 0 to up to 12 weeks will encompass the study therapy administration and evaluation phase. The precise therapy employed will be determined according to subject randomized group allocation, and the duration of the study therapy administration phase will be determined according to individual subject wound healing and status progression and safety evaluations. The study therapy administration phase will comprise the

following progressive activities, as applicable, and will be initiated in the inpatient clinic setting: therapy administration, , and weekly or standard of care wound healing and safety evaluation. The study therapies are delivered in continuous mode throughout the individual subject's entire study therapy administration phase; with the only consistent interruption being for the three times a week wound dressing changes. There will likely be other minimal daily interruptions such as to allow for subject showering and bathing. Therapy administration phase will continue until study wound is ready for closure by secondary intention, after which time the therapy will be discontinued.

Therapy Administration

- Therapy phase to be continued until wound is ready for closure by secondary intention
 - During this therapy administration phase, all subjects will receive NPWT therapy for 4 weeks or until the wound is deemed ready for surgical closure, whichever occurs first. This time point will serve as the individual subject's study evaluation endpoint.
 - Study wound readiness for surgical closure in this study is defined as the time point (evaluation visit) at which the following three factors pertaining to the status of the study wound are determined to co-exist by the study investigator:
 - deep structures (bone, tendon, joint) are covered with granulation tissue
 - the wound depth is < 2 mm
 - the wound bed is ready for skin graft, delayed primary closure or rotational flap to cover the defect.

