 - It is anticipated that most wounds will be determined ready for surgical wound closure by 4 weeks of therapy administration; however this may occur as early as after 2 weeks or subjects may be followed up to the full 12 weeks, and closure may occur anywhere inbetween (to be determined by investigator). It is also possible for some subjects that the wound may not be ready for closure even after 12 weeks. These subjects will be discharged from the study at that time and continue appropriate care for their wound with their physician.
 - The surgical wound closure procedure is performed in the operating room, using the most applicable of the following common mechanisms for closure, as is optimal for the individual subject and wound: delayed primary closure, rotational flap to close the wound, split thickness skin graft.
- Post Wound Closure Evaluation Phase
 - Following surgical closure of the wound, the subject will enter the post wound closure evaluation phase. This phase will last up to week 12 following study enrollment and therapy administration start, such that the duration of the post wound closure evaluation phase will vary for each subject according to the time point at which their wound was deemed ready for surgical closure. For example, a subject whose wound is surgically closed after week 4 of the therapy administration phase will enter a post wound closure evaluation phase that spans from week 5 through week 12, at which time the subject will exit the study. A subject whose wound does not close sufficiently for surgical repair by week 12 will exit the study at that time without entering the post wound closure evaluation phase.
 - The post wound closure evaluation phase will comprise weekly or standard of care evaluations in the outpatient clinic setting. If the wound remains closed with no sign of re-opening or infection, no further efficacy or safety evaluations will be taken at that visit. At post therapy

administration phase completion (as applicable to the individual subject), a standard of care blood draw will again be taken as at the baseline evaluation to assess lab markers.

- If at any of the post wound closure evaluation visits, the wound is found to have re-opened and/or shows signs of infection, the following will occur at the discretion of the physician:
 - Measurements of dehiscence will be taken
 - Surgical debridement of the wound will be done
 - NPWT only will be reapplied per standard of care

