Wound Assessment/ Debridement	X	X	X		X		
Tissue /bone ¹ / wound culture samples for qPCR cultures & bioburden analysis		X	X (Subsequent surgery)				

			while Inpatient)				
NPWT/NWPT (i) randomization/dressing application/changes		X	X	X (Weeks 2-4)	X (Weeks 2-4)		NWPT for maximum 4 weeks after baseline(Day0 surgery) if wound is not closed in the hospital
SF-36 Questionnaire	X					X	
Hyperspectral Imaging Analysis	X						To occur prior to surgery
Discharge Instructions			X		X		
Offloading			X	X	X		At hospital discharge & continuing to Week 12
Adverse Events		X	X	X	X	X	
Current/concomitant antibiotics	X	X	X	X	X	X	
Wound imaging/measurement		X	X		X	X	While active study wound is present
Neuropathy Disability Score in Patients with Diabetes	X						

¹ Only if performed as a necessary part of standard of care.

² Subjects who heal before week 12 will exit the study and complete EOS visit.

Biostatistics

Sample Size Justification:

There are no published data with the Cardinal PRO negative pressure wound therapy (NPWT) device with or without irrigation in order to determine an estimate of the sample size for this study. One of the purposes of this project is to obtain data, so we can power a larger multicenter study. Even though the KCI NPWT device with irrigation has been commercially available, there is little data about volume change or wound healing in the population we are studying.

The previous sample size justification was based on a comparison of the proportion of wounds expected to achieve surgical closure. The proportion of subjects with closed wound was 62% using traditional KCI NPWT and 94% using NPWT with periodic irrigations with Prontosan. For the sample size, we estimated 85-90% wound closure with NPWT with irrigation and 60% wound closure with NPWT without irrigation. We assume the NPWT devices (KCI and Cardinal) without irrigation would have similar results.

Equations

The following formula was used to estimate the required sample size, n , for the relative difference in proportions P_1 and P_2 .

$$n = \frac{\left(Z_{\alpha/2} \sqrt{2P(1-P)} + Z_{\beta} \sqrt{P_1(1-P_1) + P_2(1-P_2)} \right)^2}{(P_1 - P_2)^2}$$

where

$$P = \frac{P_1 + P_2}{2}$$

Using the formula above and assuming 90% wound closure with NPWT with irrigation and 60% wound closure with NPWT without irrigation and a type I error of 0.1, the required sample size is about 25. If a Type I error of 0.05 is assumed, then the required sample size is about 31.

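### The protocol gives incompatible end rules for NPWT, so the length of therapy is undefined for any wound not ready for closure at week 4

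*Combined protocol and SAP*

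**What the plan says.** The protocol ends NPWT in three different ways.

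- **Four-week cap, all arms.** Therapy Administration: "all subjects will receive NPWT therapy for 4 weeks or until the wound is deemed ready for surgical closure, whichever occurs first". The next sentence makes that time point the subject's study evaluation endpoint. The Schedule of Events note agrees: "NWPT for maximum 4 weeks after baseline(Day0 surgery) if wound is not closed in the hospital". The NPWT row of the Schedule marks the home-health and clinic columns for weeks 2-4 only.
- **Until readiness, all arms, no week limit.** Procedures and Evaluations During the Research: "Therapy administration phase will continue until study wound is ready for closure by secondary intention, after which time the therapy will be discontinued", with "The study therapies are delivered in continuous mode throughout the individual subject's entire study therapy administration phase". The outer window is wider than the cap: "The time period from Day 0 to up to 12 weeks will encompass the study therapy administration and evaluation phase". The Randomization section keeps subjects on their assigned therapy until the investigator judges the wound ready. Home Health Visits continues NPWT (without irrigation) at home when the wound is not ready at discharge. Neither section names a week.
- **Until closure, KCI arm only.** Control Devices: "Subjects in the KCI arm of this clinical study will receive NPWT alone (standard of care) until wound closure". Neither PRO arm has a matching sentence.

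Therapy Administration expects most wounds to be ready by 4 weeks. It also provides for readiness at any time up to week 12, or not at all: "A subject whose wound does not close sufficiently for surgical repair by week 12 will exit the study at that time".

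**The concern.** How long the randomised treatment is given should be fixed by the protocol and should be the same in every arm unless duration is itself under test. Here study staff facing a wound that is not ready at week 4 have instructions to stop and instructions to continue. The readiness judgement is the investigator's and the trial is open-label, so the choice could depend on the device in use.

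Three analyses could be affected. PRO versus KCI is a non-inferiority comparison with a 10% margin, and unequal duration would mix device with length of therapy. Time to close, dehiscence and recurrence are compared between arms with follow-up to week 12. The Survival Analyses Models section also plans to compare overall duration of treatment, which is hard to interpret if duration depends on which section was followed.

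**Working it through.** The plan states no exposure figure that could be reproduced, so the check sets the rules side by side and converts weeks to days.

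**1. Inputs and arithmetic.** Cap: 4 weeks × 7 = 28 days. End of the study window: 12 weeks × 7 = 84 days. Largest gap: 84 − 28 = 56 days (8 weeks). Ratio: 84 / 28 = 3.

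**2. Last day of NPWT under each rule.** Week 10 (70 days) is only an illustration.

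| Rule | Arms covered | Ready by week 4 | Ready at week 10 | Not ready by week 12 |
|---|---|---|---|---|
| 4-week cap (Therapy Administration, Schedule) | all | day of readiness | day 28 | day 28 |
| Until readiness (phase definition, Randomization, Home Health Visits) | all | day of readiness | day 70 | day 84, at study exit |
| Until closure (Control Devices) | KCI only | day of closure, possibly after readiness | day 70 or later | day 84, at study exit |

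The rules nearly agree when the wound is ready by week 4. They diverge by 70 − 28 = 42 days in the week-10 case and by 56 days at the limit.

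**3. Can the cap and the 12-week window be reconciled?** The natural attempt is 4 weeks of NPWT followed by observation to week 12. It fails on the text. Therapy is said to run through the whole therapy administration phase, and that phase is said to last until readiness. A wound first ready at week 10 is therefore still in the therapy phase, and still on therapy, after the cap has ended it. The two rules also sit in the same list: the parent bullet of Therapy Administration continues the phase to readiness, and the bullet below it imposes the 4 weeks.

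**4. Does the text itself create a difference between arms?** The cap covers all subjects, and so do the readiness rules. Only the closure rule is specific to one arm. A by-arm gap therefore needs staff to apply the closure rule to KCI subjects and the cap to PRO subjects. The wording permits this but does not instruct it.

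**5. Which outcomes are reached?** Study Objectives and Endpoints names reduction in wound volume as primary for PRO versus KCI and for PRO with versus without irrigation, but gives no reading time.

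- If volume is read at the study evaluation endpoint (4 weeks or readiness, whichever is first), NPWT given after day 28 comes after the measurement. The effect then falls mainly on time to close, dehiscence, recurrence and the duration-of-treatment comparison.
- If volume is read later, for example at the week 12 visit, exposure in weeks 5-12 enters the primary comparisons as well.

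**6. How many subjects?** The only closure rate assumed for NPWT without irrigation is 60% (Sample Size Justification). It has no time point. The 62% behind it comes from the retrospective cohort, whose closure result is described under Preliminary Studies as closure before discharge. The mean stay in that cohort's standard NPWT group was 14.9 days. It also counts wounds closed, not wounds judged ready. The proportion not ready at week 4 cannot be obtained from it.

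**The case against.** The strongest reply is that Therapy Administration fixes the evaluation endpoint at 4 weeks or readiness. Up to that point all the rules give nearly the same exposure, so the primary volume comparison is shielded. This stands if volume is in fact read then, but no section ties the primary endpoint to that time point.

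A reader might infer that the protocol plans longer therapy for the KCI arm. The documents do not support that. The cap applies to all subjects, KCI included, and the Randomization section's open-ended rule applies to every arm. The KCI sentence is an isolated mismatch, and a difference by arm is a possibility only. Nor does the conflict arise from several sites following different sections, since this is a single-center trial. The same staff would be choosing among instructions.

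A reader might also infer that the conflict favors a false claim of non-inferiority. That does not follow. If longer NPWT helps healing (an assumption) and KCI subjects received more of it, PRO would be disadvantaged and non-inferiority would be harder to show. The direction depends on how staff resolve the conflict.

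Finally, most wounds are expected to be ready by 4 weeks. That limits the reach of the problem, but the protocol provides explicitly for the remainder.

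**Conclusion.** Wrong as written: an internal contradiction in how long the randomised treatment lasts. For a wound not ready at week 4 the rules cannot all be followed, and the possible end of NPWT within the study ranges from day 28 to day 84, up to 56 days apart. That size rests only on the stated 4 and 12 weeks.

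The effect on outcomes followed to week 12 and on the duration-of-treatment comparison holds under either reading of the volume endpoint. The effect on the PRO versus KCI non-inferiority comparison is conditional on volume being read after the 4-week-or-readiness point. Imbalance between arms is possible, not planned.

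It is tempting to size the problem as 12 subjects in each non-irrigation arm: 90 / 3 = 30 per arm, and 30 × (1 − 0.60) = 12. The documents do not support that count, because the 60% is not a week-4 readiness rate. No number affected is claimed here.

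**What to change.** - Reconcile Randomization, Control Devices, Procedures and Evaluations During the Research, Therapy Administration, Home Health Visits and the Schedule of Events into one NPWT end rule, in identical words for all three arms. The duration itself is for the sponsor and investigator to choose.
- State whether the 4-week-or-readiness time point is when the primary volume endpoint is read.
- Make sure NPWT start and stop dates are captured for every subject. The case report form is not among the documents, and the planned duration comparison suggests that they may already be collected.
- Report days on NPWT by arm beside the primary comparison.

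The cost is amendment wording and one small descriptive table. Depending on the rule chosen, current handling of slow-healing wounds may have to change.
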